7.1. Control arm

	Screening	Baseline Visit ¹	Treatment						End of Treatment ⁷	End of Study
Weeks (w)	-2w ~ 0d	0	1w	2w	4w	8w	12w~ (Every 4w)	52w~ (Every 2month)	80w~	24month
Visit window	n-a	n-a	±4d	±4d	±1w	±2w	±2w	±2w	±2w	±2w
Consent	O									
Randomization		O								
Medical history	O									
Physical Exam	O		O	O	O	O	O	O	O	O
Neurologic exam	O									
Sputum AFB smear	O ⁵	O ⁵	O	O	O	O	O	O	O	O
TB culture (solid)	O ⁵	O ⁵	O	O	O	O	O	O	O	O
TB culture (liquid)	O ⁵	O ⁵	O	O	O	O	O	O	O	O
Genotypic DST	If available									
Phenotypic DST ²	With first/reverted cultured M.TB									
Chest X-ray (CXR)	O ⁵	O ⁵	O ⁸	O ⁸	O	O	O	O	O	O
Chemistry, Electrolyte	O ⁵	O ⁵	O	O	O	O	O	O	O	
Complete blood count	O ⁵	O ⁵	O	O	O	O	O	O	O	
ECG	O ⁵									
Urine HCG ³	O	O								
HIV, HBV ⁴		O ⁵								
Optic test	O									
Compliance of drug intake			O	O	O	O	O	O	O	
Adverse drug reaction			O	O	O	O	O	O	O	
Other medication ⁶	O	O	O	O	O	O	O	O	O	

¹Administration of anti-TB regimen can begin at baseline visit since drug-resistant TB must be treated immediately.

²Drug susceptibility test for isoniazid, rifampicin, ethambutol, pyrazinamide, streptomycin, kanamycin, amikacin, capreomycin, ofloxacin, levofloxacin, moxifloxacin, prothionamide, cycloserine, and para-aminosalicylic acid (omit for patients with results already provided).

³Only for childbearing age (the blood HCG test result can be extracted)

⁴Study drugs can be administered before the obtaining of results since eligibility is not determined by these results.

⁵Could be skipped if previous tests except ECG were done within four weeks. In case of ECG, within 1week.

⁶Check prohibited drugs for exclusion criteria at screening visit, and check immunosuppressants including steroids after enrollment.

⁷End of treatment(EOT) visit will be determined by the standard TB treatment guidelines. If EOT visit and the end of study(EOS) visit are the same, a test corresponding to the EOT visit will be conducted.

⁸Could be skipped if previous CXR test was performed within 2 weeks

7.2. Investigational arm

	Screening	Baseline Visit ¹	Treatment					End of Treatment ⁷	Treatment completion to End of Study
Weeks (w)	-2w ~ 0d n-a	0 n-a	1w	2w	4w	8w	12w ~ (Every 4w)	40w ~ 52w	~ 24month (Every 2month) ±2w
			±4d	±4d	±1w	±2w	±2w	±2w	
Consent	O								
Randomization		O							
Medical history	O								
Physical Exam	O		O	O	O	O	O	O ⁷	
Neurologic exam	O		O	O	O	O	O	O ⁷	
Sputum AFB smear	O ⁵	O ⁵	O	O	O	O	O	O	O
TB culture (solid)	O ⁵	O ⁵	O	O	O	O	O	O	O
TB culture (liquid)	O ⁵	O ⁵	O	O	O	O	O	O	O
Genotypic DST	If available								
Phenotypic DST ²	With first/reverted cultured M.TB								
LZD, Delamanid resistance examination	If needed (please see the protocol section 9.0)								
Chest X-ray (CXR)	O ⁵	O ⁵	O ⁸	O ⁸	O	O	O	O	O
Chemistry, Electrolyte	O ⁵	O ⁵	O	O	O	O	O	O ⁷	
Complete blood count	O ⁵	O ⁵	O	O	O	O	O	O ⁷	
ECG	O ⁵	O ⁵	O	O	O	O	O	O ⁷	
Urine HCG ³	O	O	O	O	O	O	O	O ⁷	
HIV, HBV ⁴		O ⁵							
Optic test	O	O	O	O	O	O	O	O ⁷	
Compliance of drug intake			O	O	O	O	O	O ⁷	
Adverse drug reaction			O	O	O	O	O	O ⁷	
Other medication ⁶	O	O	O	O	O	O	O	O ⁷	

¹Administration of anti-TB regimen can begin at baseline visit since drug-resistant TB must be treated immediately.

²Drug susceptibility test for isoniazid, rifampicin, ethambutol, pyrazinamide, streptomycin, kanamycin, amikacin, capreomycin, ofloxacin, levofloxacin, moxifloxacin, prothionamide, cycloserine, and para-aminosalicylic acid (omit for patients with results provided already).

³Only for childbearing age (the blood HCG test result can be extracted).

⁴Study drugs can be administered before the obtaining of results since eligibility is not determined by these results.

⁵Could be skipped if previous tests except ECG were been done within four weeks. In case of ECG, within 1week.

⁶Check prohibited drugs for exclusion criteria at screening visit, and check immunosuppressants including steroids after enrollment.

⁷End of treatment visit will be determined by the time of culture conversion. Omit test after end of treatment (EOT) visit.

⁸Could be skipped if previous CXR test was performed within 2 weeks

Confidential

MDR-END v14.0, 20Mar2020

8. Screening and Procedures

8.1. Subject Screening and Enrollment

- When resistance to rifampicin is confirmed, screening can be done after subject signs the consent form.
- Recording of medical history, physical examinations and neurological examinations will be performed. Sputum AFB smear microscopy, MTB culture on both liquid and solid media will be performed.
- Genotypic DST (MTBDRsl and etc.) could be performed, if available.
- Phenotypic DST will be performed for the first positive culture and reversion specimen if available.
- Chest X-ray (CXR), Electrocardiogram (ECG), complete blood count, electrolytes, chemistry (glucose, albumin, total bilirubin, AST, ALT, Creatinine) will be performed. The results of the test performed according to the standard TB treatment guidelines (calcium, phosphorus, uric acid, cholesterol, protein, alkaline phosphatase, BUN, etc.) can be further reviewed.

* Tests could be skipped in case of having available results or tests were performed recently within four weeks (In case of ECG, within a week). It is possible to extract chest CT results instead of chest X-ray(CXR) test.

- For subject of childbearing potential, urine HCG will be performed (the blood HCG test result can be extracted).

8.2. Randomization

- Once a subject has signed informed consent form and found eligible, subject will be randomly assigned to investigational or control arm at a rate of 1:1 on week 0.
- The study will use block randomization method, using block sizes of 4 or 6 chosen randomly, stratified by ①presence/absence of cavitation on baseline chest radiographs, ②presence/absence of baseline diabetes mellitus. Randomization table will be prepared by using SAS 9.3.
- Randomization table and web-based randomization is operated by the person in charge of this clinical trial at the Medical Research Collaborating Center (MRCC) in Seoul National University Hospital Biomedical Research Institute. The access and management of randomization information will be carried out independently from the clinical investigator or clinical trial sponsor.
- Diabetes mellitus will be diagnosed for one of the following three. ① fasting blood glucose \geq 126mg/dL ② random blood glucose \geq 200mg/dL ③ currently taking hypoglycemics.

Confidential

MDR-END v14.0, 20Mar2020

8.3. Baseline Visit and Beginning of Treatment

- AFB smear microscopy, and MTB culture on liquid and solid media of sputum or bronchoscopic specimen will be performed.
- CXR, ECG, complete blood count, electrolytes, chemistry (albumin, total bilirubin, alkaline phosphatase, AST, ALT, Creatinine), anti-HIV antibody and HBsAg will be performed.
- Ishihara Test for Color-blindness will be performed to check baseline abnormalities of color blindness.

* Tests could be skipped in case of having available results or tests were performed recently within four weeks (In case of ECG, within a week).

* Study drugs can be administered before the obtaining of anti-HIV Ab, HBsAg, and alkaline phosphatase results since eligibility is not determined by these results.

* Administration of anti-TB regimen can begin at baseline visit since drug-resistant TB must be treated immediately.

8.4. Study Visits

- Subjects will visit for study at 1 week, 2 weeks and 4 weeks after enrollment, and then every four weeks until 12 months(52 weeks), afterwards every 2 months until the end of treatment (EOT). The time of EOT is 40 or 52 weeks for the Investigational arm and will be determined individually for control arm according to the standard of care treatment.
- Subjects in the investigational arm will visit every 2 months after EOT even if it is before 12 months(52 weeks).

8.4.1. Study tests of visits while on anti-TB medication

- ① Control arm
 - Physical examination
 - Sputum AFB smear microscopy and MTB culture on liquid and solid media
 - CXR
 - Complete blood count, chemistry (total bilirubin, alkaline phosphatase, AST, ALT, creatinine)

Confidential

MDR-END v14.0, 20Mar2020

- Check taking systemic steroid and immunosuppressive agents.

② Investigational arm

- Physical examination, neurological examination
- Sputum AFB smear microscopy and MTB culture on liquid and solid media
- CXR, ECG
- Complete blood count, electrolyte, chemistry (total bilirubin, albumin alkaline phosphatase, AST, ALT, creatinine)
- Ishihara Test for Color-blindness to detect occurrence of color vision abnormalities.
- Check all other concomitant medications including systemic steroid and immunosuppressive agents.
- For subject of childbearing potential, urine HCG will be performed (the blood HCG test result can be extracted).

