5.1.2. Multicenter, randomized, open-label, two arms, phase II/III clinical trial

- Once eligibility is confirmed and the subject consents for participation, he/she will be randomly assigned to the following two groups at 1:1.

① Group 1 (Control arm)

Treatment will be according to the 2014 Korean guidelines for the treatment of tuberculosis (19) and 2014 WHO guidelines (20). Treatment principles are summarized as follows.

- Combination of treatment regimen
 - Intensive phase regimen comprising four effective second-line anti-TB drugs (including an injectable) and pyrazinamide.
 - It is recommended that at least five active drugs be used, selected appropriately based on drug susceptibility testing (DST) results.
 - Example of regimen: pyrazinamide, a fluoroquinolone, cycloserine, prothionamide, and an injectable
 - Efforts should always be made to use a fluoroquinolone, preferentially use levofloxacin or moxifloxacin.
 - Cycloserine should be used preferentially, but when it is not possible para-aminosalicylic acid (PAS) could be used.
 - The medication like linezolid, delamanid, or bedaquiline can be added from the beginning of the treatment if the patient has a resistance to injectables. In addition, linezolid, delamanid, or bedaquiline can be used to fortify the regimen when the adverse drug reactions occur to other anti-TB drugs.
 - The usage and dosage follow 2014 Korean guidelines for the treatment of tuberculosis published by the Committee for the Revision of Korean Guidelines for Tuberculosis and the Korea Centers for Disease Control and Prevention (19) but not limited to it.

Type of Drug	Dose		
	Usual dose	Maximal dose	Usage
Ethambutol	15-20mg/kg	1600mg	Once, before or after

Confidential

MDR-END v14.0, 20Mar2020

			meal
Kanamycin Amikacin Streptomycin Capreomycin	15mg/kg, < 50 years 10mg/kg, ≥ 50 years	1000mg, < 50 years 750mg, ≥ 50 years	Once
Cycloserine	500mg, < 50 kg 750mg, 50-70 kg 750-1000mg, >70 kg	1000mg	Once or divide in two, before or after meal (best to take on an empty stomach)
Prothionamide	500mg, < 50 kg 750mg, 50-70 kg 750-1000mg, >70 kg	1000mg	Once or divide in two, after meal
PAS	150mg/kg	12g	Divide in two or three after meal

- Treatment duration

- Intensive phase is recommended to be a minimum of 8 months.
- Total treatment duration is recommended to be 20 to 24 months.

② Group 2 (Investigational Group)

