Regimen consists of only oral medication using delamanid, linezolid, levofloxacin, and pyrazinamide, for nine or twelve months.

- Treatment duration

- A total of 9 months (40 weeks) when sputum culture conversion to negative occurs within three months of treatment
- A total of 12 months (52 weeks) when sputum culture conversion to negative occurs between 3 and 6 months of treatment

- Combination of treatment regimen

- Delamanid, 200mg/day (100mg bid)
 - Use for the entire treatment period unless it must be stopped for reasons such as adverse events.
- Linezolid
 - 600mg/day during the first two months
 - 300mg/day afterwards until the end of treatment

Confidential

MDR-END v14.0, 20Mar2020

- If linezolid re-administration is required after temporary discontinuation due to adverse events, the dose reduction to 300mg is allowed even within two months of treatment.
- Levofloxacin
 - $\leq 50\text{kg}$, 750mg/day
 - $>50\text{kg}$, 1000mg/day
 - Can be reduced or substituted with moxifloxacin due to reasons such as adverse events, and at this time, QT prolongation should be observed closely. Also, this substitution will not be considered as a drug change since both are fluoroquinolones of similar potency.
 - Once a day
- Pyrazinamide
 - $<50\text{kg}$, 1000mg/day
 - 50-70kg, 1500mg/day
 - $>70\text{kg}$, 2000mg/day
 - Can be reduced due to adverse event. Even if pyrazinamide resistance is discovered on the phenotypic drugs susceptibility testing after commencing treatment, it can be continued (20).
 - Once or divide in two or three

Since the definition of treatment outcomes follows the 2014 WHO Guidelines (20), as described in the ‘Research Protocol 6. Definition’, the change of a drug is allowed according to medical judgments, such as adverse drug reactions. However, the change of two or more drugs is considered ‘treatment failed’ and the participants will be withdrawn from the study.

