5.3. Secondary Outcomes

- Time to sputum *Mycobacterium tuberculosis* (MTB) culture conversion to negative (liquid and solid culture media)
- Sputum MTB culture conversion proportion at two months of treatment (liquid and solid culture media)
- Sputum MTB culture conversion proportion at six months of treatment (liquid and solid culture media)
- AE of grade 3 and higher
- Proportion of participants with a treatment success at the end of treatment.
- Proportion of relapse after treatment success (investigational arm)
- Proportion of death and time-to-death
- Comparison of treatment success rates between treatment groups according to pyrazinamide resistance.

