In order to check if there is any significant difference in demographic or clinical characteristics among the two arms prior to administration of study drugs, the serial data is summarized as mean, standard deviation, median and minimum and maximum, and the two arms are compared by independent t-test or Wilcoxon rank sum test. For categorical variables, the frequency and proportion per group is found and the two arms are compared by Chi-square test and Fisher's exact test. This analysis is carried out on the ITT analysis group.

4) Efficacy Evaluation

All statistical analysis of the two arms is carried out at significance level of 5% for both sides unless stated otherwise. For additional analysis, stratified analysis will be performed for primary and secondary outcome evaluation by stratification into sputum smear positive patient groups and sputum smear negative patient groups based on the sputum smear microscopy results.

① Primary Efficacy Evaluation

The primary outcome of this clinical trial is treatment success rate at 24 months after the initiation of treatment.

Describe the treatment success rate of the control arm and the investigational arm with a two-sided 95% confidence interval. Then, in order to test for non-inferiority of the investigational arm, when the lower limit of one-sided 97.5% confidence interval of the difference ($P_T - P_C$) between control and investigational arm is larger than the non-inferiority margin of -10%, it is concluded that the treatment success rate of the investigational arm is non-inferior to the treatment success rate of the control arm. The subjects whose treatment result is assessed 'Not accessible' are excluded from the primary outcome evaluation.

② Secondary Efficacy Evaluation

The secondary outcomes are analyzed as following and describe at exploratory levels.

- **Time to sputum culture conversion after the initiation of treatment (liquid and solid culture media)**

- In order to test whether the time to sputum culture conversion after the initiation of treatment of the control arm and investigational arm (liquid and solid culture media) are different statistically, the median time is estimated in each group using the Kaplan-Meier method, and the difference of the distribution of time to culture conversion of the two arms is compared using the Log-rank test.

- **Sputum culture conversion proportion at two months of treatment (liquid and solid culture media)**

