- In order to test whether there is a statistical difference in sputum culture conversion proportion at two months of treatment between the control arm and the investigational arm (liquid and solid culture media), each arm is summarized by conversion frequency and proportion, and the sputum culture conversion proportions at two months between the two arms are compared using the Chi-square test and Fisher's exact test.

- **Sputum culture conversion proportion at six months of treatment (liquid and solid culture media)**

- In order to test whether there is a statistical difference in sputum culture conversion proportion at six months of treatment between the control arm and the investigational arm (liquid and solid culture media), each arm is summarized by conversion frequency and proportion, and the sputum culture conversion proportions at six months between the two arms are compared using the Chi-square test and Fisher's exact test.

Confidential

MDR-END v14.0, 20Mar2020

- **Proportion of treatment success at the end of treatment**

-Summarize the frequency and proportion of treatment success at the end of treatment in the investigational arm.

- **Proportion of relapse after treatment success**

-Summarize the frequency and proportion of relapse after treatment success in the investigational arm.

- **Proportion of deaths and time-to-death**

-Summarize the frequency and proportion of death in the investigational arm, and estimate median survival time using the Kaplan-Meier method.

- **Primary outcome evaluation between treatment groups according to pyrazinamide resistance**

-Presentation of treatment success rate in the control arm and the investigational arm in small groups according to the presence or absence of pyrazinamide resistance, and verification of non-inferiority of treatment success rate difference between the treatment groups

5) Safety Evaluation

Safety evaluation is performed using adverse events that occur during the clinical trial period. Summarize all adverse events and serious adverse events, adverse event frequency and percentage, and 95% confidence interval on it. Also, summarize and evaluate the occurrence rate of adverse events in relationship to the study drug and severity. The incidence of adverse events (CTCAE Grade 3 and above toxicity) between the two arms are compared using the Chi-square test or Fisher's exact test.

11. Safety Assessment

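### ECG, neurological and colour-vision tests are scheduled on treatment in the investigational arm only, so part of the grade 3 or higher adverse event comparison reflects unequal detection; control electrolytes and albumin are also inconsistently specified

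*Combined protocol and SAP*

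**What the plan says.** **The outcome.** Protocol 5.3 lists "AE of grade 3 and higher" as a secondary outcome. Protocol 10.2 states: "The incidence of adverse events (CTCAE Grade 3 and above toxicity) between the two arms are compared", by chi-square or Fisher's exact test. SAP Table 23 repeats this in the mITT, PP and safety sets. Tests in the efficacy part of 10.2 are "carried out at significance level of 5% for both sides unless stated otherwise"; I take the safety tests to use the same level. Protocol 11.1 counts abnormal laboratory and diagnostic test results as adverse events.

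**The tests.** The investigational list in 8.4.1 includes neurological examination, ECG, electrolytes, albumin and the "Ishihara Test for Color-blindness to detect occurrence of color vision abnormalities". The investigational schedule (7.2) marks ECG, neurological and optic tests at every on-treatment visit up to end of treatment. The control schedule (7.1) marks each of the three once, at screening. Section 8.3 lists ECG and Ishihara at baseline without distinguishing arms, but baseline is not an on-treatment visit.

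**Control bloods.** The 7.1 row "Chemistry, Electrolyte" is marked at every control on-treatment visit. The control list in 8.4.1 reads "Complete blood count, chemistry (total bilirubin, alkaline phosphatase, AST, ALT, creatinine" and ends there, without electrolytes or albumin. Section 8.5, item 9, includes both for everyone.

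**Control drugs.** On the control arm, 5.1.2 says: "The medication like linezolid, delamanid, or bedaquiline can be added from the beginning of the treatment if the patient has a resistance to injectables". These drugs may also strengthen the regimen after adverse reactions to others, and moxifloxacin is one of two preferred fluoroquinolones. When moxifloxacin is substituted in the investigational arm, "QT prolongation should be observed closely". Section 5.6.2 lists moxifloxacin and bedaquiline among drugs needing QT caution alongside delamanid.

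**The concern.** If a test result can itself be an adverse event, the count depends on how often the test is done. A QT, sensory or colour-vision abnormality can be found by schedule in one arm. In the other it is found only if it causes symptoms, is reported, or turns up on an unscheduled test. These are relevant events: the delamanid table in 5.6.3 lists QT prolongation as very common and peripheral neuropathy as common. (Those are not grade 3 or higher frequencies.) A difference in Table 23 could then be read as a difference in toxicity when part of it is a difference in looking.

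The electrolyte mismatch is a separate problem. Sites can follow either section, and SAP Table 29 needs control electrolytes and albumin whichever they follow.

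**Working it through.** The plan states no figure on this point, so there is none to reproduce. The check is a count, a comparison of sections and an illustration.

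**1. Scheduled tests on treatment** (7.1, 7.2, 8.4)

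- 40-week course: weeks 1, 2, 4, 8, then 12 to 40 every 4 weeks (8 visits): 4 + 8 = 12 of each test.
- 52-week course: add weeks 44, 48 and 52: 12 + 3 = 15 of each.
- Control: 0 of each.

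**2. Which events are affected.** Physical examination, blood count, core chemistry and an adverse reaction check are scheduled on treatment in both arms. Unequal detection is therefore confined to events that ECG, neurological examination or Ishihara plates can find. Electrolyte events join them only if the 8.4.1 control list is the one followed.

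**3. Direction.** Control treatment runs 20 to 24 months. Adverse reaction checks number 15 to week 52, then one every 2 months: 4 more by month 20 (months 14, 16, 18, 20) or 6 by month 24. That is about 19 to 21, against 12 or 15 in the investigational arm, where scheduled safety tests stop at end of treatment (7.2, footnote 7). More tests raise the investigational count and longer observation raises the control count.

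**4. Illustration; every rate is assumed.** Let true toxicity be equal. Let *b* be the grade 3 or higher rate detectable in both arms (20%, 30%, 40%). Let *x* be the share of participants whose only such event shows on a scheduled test alone, and *d* the fraction of those events that control detects anyway.

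- Investigational rate = *b* + *x*; control rate = *b* + *d·x*; spurious difference = *x*(1 − *d*).
- Chance of p < 0.05: the sum of Bin(*i*; *n*, *b* + *x*) × Bin(*j*; *n*, *b* + *d·x*) over all pairs (*i*, *j*) with |z| > 1.96, where z = (*i*/*n* − *j*/*n*)/√[2*p̄*(1 − *p̄*)/*n*] and *p̄* = (*i* + *j*)/(2*n*).
- *n* = 48 is the plan's number per arm before inflation; *n* = 102 is the number randomised per arm.
- Example: *n* = 102, *b* = 30%, *x* = 5%, *d* = 0 gives 35% against 30%, a 5-point difference, and a chance of 11.8%.

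| *x* | *d* | Spurious difference | Chance, *n* = 48 | Chance, *n* = 102 |
|---|---|---|---|---|
| 0 | – | 0 | 4.9–5.2% | 4.9–5.4% |
| 2% | 0 | 2 points | 5.4–5.8% | 6.1–6.5% |
| 2% | 0.5 | 1 point | 5.1–5.3% | 5.2–5.7% |
| 5% | 0 | 5 points | 7.9–9.0% | 11.8–13.5% |
| 5% | 0.5 | 2.5 points | 5.8–6.0% | 6.6–7.3% |
| 10% | 0 | 10 points | 16.8–20.5% | 32.1–37.8% |
| 10% | 0.5 | 5 points | 7.9–8.7% | 11.6–12.6% |

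Ranges run over the three values of *b*. The illustration leaves out the longer control observation in step 3.

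**5. Control tests against the SAP tables**

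| Item, control arm on treatment | 7.1 | 8.4.1 | 8.5 | SAP output |
|---|---|---|---|---|
| Electrolytes | every visit | omitted | included, no arm distinction | Table 29, both arms |
| Albumin | not itemised | omitted | included, no arm distinction | Table 29, both arms |
| Neurological examination | none after screening | omitted | as a general procedure | Table 28, shift to End of Study, both arms |

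The Table 28 control shift has no scheduled examination behind it. In the investigational arm the last scheduled one is at end of treatment, not End of Study.

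**The case against.** The strongest reply is that this is an ordinary limitation of an open-label trial in which a new regimen is watched more closely. Most of the grade 3 or higher comparison rests on assessments common to both arms. Control detection need not be zero: 8.5 allows further neurological tests once a neurological event has developed and lets standard-of-care results be used. The documents give no rate at which an ECG or colour-plate finding reaches grade 3 without clinical signs. SAP Table 25 already shows events by preferred term and grade in each arm, so a reader can pick out the affected ones. All of this stands, and it limits the point. It does not remove it, because Table 23 still gives a p-value for the total with no allowance for unequal testing.

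Three stronger readings are tempting, and the documents do not support them.

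- A reader might infer that the safety comparison is uninterpretable. Only three kinds of event are affected, and the illustrated distortion is small when few events are test-only or when control detects half of them.
- A reader might infer a bias against the new regimen. The extra tests push that way, but control observation is longer and the net effect cannot be derived.
- A reader might infer that the QT passages contradict each other. The caution on moxifloxacin in 5.1.2 concerns substitution in the investigational arm, 5.6.2 is a precaution list that sets no ECG schedule, and 7.1 does not forbid clinically indicated ECGs. What they show is a gap in scheduled monitoring between arms.

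It is also tempting to sort events by how they were first detected and to test only those not found by an investigational-only test. That would create a new bias. A neuropathy first picked up at a scheduled investigational examination would leave the tested set, while the same neuropathy presenting clinically in control would stay in.

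**Conclusion.** The point holds in limited form. Scheduled on-treatment ECG, neurological and Ishihara tests number 12 or 15 of each in the investigational arm and 0 in control, and the grade 3 or higher test makes no allowance for this. The effect is confined to QT, neurological and colour-vision events. Its size cannot be computed from the documents and its net direction is uncertain. The illustration shows only when it would matter. With equal true toxicity and no control detection, a 2-point shift leaves the false-positive rate near nominal, while a 10-point shift raises it to about 17–21% at 48 per arm and 32–38% at 102. Those shifts are assumptions.

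Two documentary defects stand without any assumption. Protocol 8.4.1 disagrees with 7.1 on control electrolytes and with 8.5 on electrolytes and albumin, while SAP Table 29 reports both. SAP Table 28 reports a control neurological shift with no scheduled examination after screening.

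**What to change.** 1. **Sensitivity analysis.** Keep the planned all-event grade 3 or higher comparison. In SAP 3.7 and Table 23, add a pre-specified analysis that excludes a list of preferred terms fixed before analysis: QT and other ECG findings, peripheral neuropathy, optic and colour-vision events, and electrolyte events if control electrolytes turn out not to be scheduled. Apply it to both arms alike, however each event was detected. Report the excluded terms descriptively by arm with on-treatment time, and state unequal testing as a limitation.
2. **Schedules and tables.** Reconcile 7.1, 8.4.1 and 8.5 on control electrolytes and albumin, so that all sites follow one list and Table 29 can be filled. Limit the Table 28 neurological shift to participants and visits with a scheduled examination.
3. **Control drugs with QT cautions.** State that 5.1.2 allows control participants drugs for which 5.1.2 (investigational arm) and 5.6.2 give QT cautions, while 7.1 schedules no on-treatment ECG. Ask the sponsor to reconcile these sections. No monitoring rule is proposed here.

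The cost is SAP wording, a protocol clarification and one extra safety table. The sensitivity analysis will contain fewer events and be less precise, and it leaves out events that the extra monitoring exists to find. For that reason it supplements the planned comparison and does not replace it.
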